# Baseline image screening can be completed within 3 months prior to enrollment. Imaging will always be performed on the day of the procedure which will be used for core laboratory baseline for comparison at 6 months.

\* The NIH Stroke Scale score should be obtained within 24 hours after stroke in the event a subject is diagnosed with a stroke.

\*\* mRS will be obtained at all scheduled visits.

\*\*\* Cerebral angiogram is required at 6 months only; in the event of a Grade 2 or more using the Raymond Roy Scale at 6 months, a second cerebral angiogram assessment will be made at 12-month follow-up to re-assess for complete occlusion and will be reported as secondary efficacy.

\*\*\*\* CTA is required at 6 months only; in the event of a Grade 2 or more using the Raymond Roy Scale at 6 months, a second cerebral angiogram assessment will be made at 12-month follow-up to re-assess for complete occlusion and will be reported as secondary efficacy.

## Aneurysm occlusion status and Raymond Roy completed when cerebral angiograms are performed.

 Cerus Endovascular	Document Number DNQS428-01	Rev. F	Page 38 of 119
Clinical Investigation Plan	Title		
Confidential & Proprietary	Coil Assisted Flow Diversion: A prospective, single arm, multi-center study to assess the safety and performance of Neqstent in adjunctive therapy (CAFI Study)		

## 7.10 Early Withdrawal

Reasons for subject withdrawal prior to study completion shall be documented. Valid reasons for early study withdrawal include:

- Death
- AE or other medical condition that prevents study participation
- Withdrawal of voluntary consent
- Lost to follow-up (LTf)
- Termination of Study

At least three documented attempts shall be made to contact any subject who is LTF.

## 7.11 Study Termination

The Sponsor has the right to terminate the Study. Reasons for Study termination shall be documented in the Clinical Investigation Report and Close-Out Monitoring Report. Valid reasons for study termination include:

- Administrative issues mandate termination
- Interim data analyses warrant study termination
- Regulatory action mandates termination

If the study is terminated for any reason, the governing Competent Authority and Ethics Committee shall be notified as applicable. If the study is terminated, all patients will remain in follow-up per the standard of care.

## 7.12 Premature termination

The Sponsor reserves the right to discontinue the clinical trial/investigation at any stage (e.g. for safety reasons) or reduce the follow-up period with suitable written notice to the Investigator.

Possible reason(s) include:

Sponsor makes a final decision for the early termination of the clinical trial, or per DSMB recommendation

Further product development is cancelled.

Should the clinical trial be discontinued by the Sponsor, subjects will be followed up as per routine hospital practice.

In this case, the Investigator shall return all clinical trial/investigation materials (including devices) to the Sponsor and provide a written statement as to why the premature termination has taken place to the EC (if applicable) and inform subjects still participating to the trial. All applicable Clinical Investigation documents shall be subject to the same retention policy (the Investigators and/or designee(s) will be instructed to retain all study records required by the

 Cerus Endovascular	Document Number DNQS428-01	Rev. F	Page 39 of 119
Clinical Investigation Plan	Title		
Confidential & Proprietary	Coil Assisted Flow Diversion: A prospective, single arm, multi-center study to assess the safety and performance of Neqstent in adjunctive therapy (CAFI Study)		

Sponsor and regulatory authorities in a secure and safe facility, with limited access. All study material shall be stored for at least 10 years or as based on national regulations. The Investigator must request authorization from the Sponsor prior to destroying study records). Sponsor or designee will inform the CA about premature termination of Clinical Trial as per regulatory requirements

Study discontinuation:

The Study Completion/Discontinuation Form must be completed when:

- the subject is considered lost to follow-up (per the above definition) before the 24 months follow-up time point has been reached or
- the subject withdraws from the study or
- the Investigator withdraws the subject from the study or
- the subject has completed the study (at last Follow-up visit per protocol, the 24 months follow up visit).

The Sponsor shall be notified of the reason for subject discontinuation. The site will provide this information on the Study Completion/Discontinuation Form (e-CRF) and on source documents. Investigators must also report this to their EC if defined by their institution's procedure.

## 8 Adverse Events

### 8.1 Adverse Event Definitions

Definitions of Adverse Event subtypes are provided in Table 9. All AEs and device deficiencies shall be reported by the clinical site investigator on a specific case report form (CRF).

**Table 9. AE Definitions per ISO 14155:2011**

Adverse Event (AE)	
An AE is:
 
Any untoward medical occurrence in a subject, unintended disease or injury, or untoward clinical signs (including abnormal laboratory findings) in subjects, users or other persons, whether or not related to the investigational medical device.
 
Note 1: This definition includes events related to the investigational medical device or the comparator.
 
Note 2: This definition includes events related to the procedures involved.
 
Note 3: For users or other persons, this definition is restricted to events related to investigational medical devices.

--------------------	--

Clinical Investigation Plan

Title

*Confidential & Proprietary*

**Coil Assisted Flow Diversion: A prospective, single arm, multi-center study to assess the safety and performance of Neqstent in adjunctive therapy (CAFI Study)**

Adverse device effect (ADE)	
An ADE is: an AE related to the use of a medical device.
 
Note 1: This definition includes events resulting from insufficient or inadequate instructions for use, deployment, implantation, installation, or operation, or any malfunction of the medical device.
 
Note 2: This definition includes any event resulting from use error or from intentional misuse of the medical device.

Serious adverse event (SAE)	
An SAE is: an AE that
 

• led to death,

• led to serious deterioration in the health of the subject that either resulted in

○ a life-threatening illness or injury, or

○ a permanent impairment of a body structure or a body function, or

○ in-patient or prolongation hospitalization, or

○ medical or surgical intervention to prevent life-threatening illness or

○ injury or permanent impairment to body structure or body function,

• led to fetal distress, fetal death, or a congenital abnormality, or birth defect.

 
Note: Planned hospitalization for a pre-existing condition, or a procedure required by the clinical investigational plan, without serious deterioration in health, is not considered to be an SAE.

Serious adverse device effect (SADE)	
An SADE is: an ADE that has resulted in any of the consequences characteristic of an SAE.

Unanticipated serious adverse device effect (USADE)	
A USADE is: a SADE which by its nature, incidence, severity or outcome has not been identified in the current version of the risk analysis report.
 
Note: Anticipated serious adverse device effect (ASADE) is an effect which by its nature, incidence, severity or outcome has been identified in the risk analysis report.

 Cerus Endovascular	Document Number DNQS428-01	Rev. F	Page 41 of 119
Clinical Investigation Plan	Title		
Confidential & Proprietary	Coil Assisted Flow Diversion: A prospective, single arm, multi-center study to assess the safety and performance of Neqstent in adjunctive therapy (CAFI Study)		

## 8.2 Adverse Event Classification

### 8.2.1 AE Severity:

The severity of an AE is a qualitative judgment of the degree of intensity, as determined by the Investigator or as reported by the subject. The severity of the AE shall be evaluated according to the following scale:

- **Mild** - no limitation of usual activities, no therapy or only symptomatic therapy required to treat the injury or illness.
- **Moderate** - some limitation of usual activities or specific therapy is required.
- **Severe** - inability to carry out usual activities, hospitalization, emergency treatment, life threatening events, or death.

The assessment of severity shall be made independent of the relationship to the device and therapy or the seriousness of the event.

### 8.2.2 AE causality:

Each AE shall be assessed by the Investigator for its relationship to the use of the study device or study procedure as follows.

- **Device Related:** Restricted to the study device.
- **Procedure Related:** Restricted to the implant procedure and any procedure associated directly with placement of the device.
- **Definitely related:** An AE is definitely related to a specific category if it is obvious, certain or there is little doubt regarding the relationship.
- **Possible related:** An AE is possibly related to a specific category if it is capable of being related but relatively unlikely.
- **Not related:** An AE is not related to a specific category if it is determined that there is no plausible association.

Subjects experiencing AEs shall be offered comprehensive medical care for conditions associated with the implant procedures and followed until their medical outcomes are resolved.

 Cerus Endovascular	Document Number DNQS428-01	Rev. F	Page 42 of 119
Clinical Investigation Plan	Title		
Confidential & Proprietary	Coil Assisted Flow Diversion: A prospective, single arm, multi-center study to assess the safety and performance of Neqstent in adjunctive therapy (CAFI Study)		

**Table 10. AE Categorization**

AEs	Non-Device-Related	Device-Related		Device Deficiencies*
Non-Serious	AE	ADE		Without SADE potential
Serious	SAE	SADE		With SADE potential
		Anticipated	Unanticipated	
		ASADE	USADE	

\* Device deficiency is the inadequacy of a medical device related to its identity, quality, durability, reliability, safety or performance. This may include malfunctions, misuse, errors, inadequate labeling

## 8.3 Adverse Event Reporting

The timely and complete reporting of AEs is essential for the risk management process. Monitoring and documentation of all AEs will allow the Sponsor to identify potential ADEs and to adhere to regulatory requirements.

The Investigative Site shall report all SAEs including USADEs and device deficiencies to the study sponsor or the sponsor's designee within 48 hours of occurrence.

All AEs shall be documented in the patient's medical record by the PI and reported by the PI using the AE CRFs. AE definitions and categories are described in Section (8), the Monitors shall confirm that the AEs are correctly categorized and entered onto the AE CRFs. The Monitor shall confirm that the AEs are consistent with the source documents.

The sponsor is responsible for submitting reports to the Competent Authority as required by the applicable regulations and guidelines. The investigator is responsible for reporting safety information to the ECs according to the ECs requirements.

# 9 Study Oversight

## 9.1 Clinical Events Committee (CEC)

A combined CEC/DSMB Committee will be established by Cerus Endovascular or designee to assess, review and classify all neurologic, device-related and procedure-related SAEs to ensure they are reported accurately. The CEC member(s) appointed for the study will be qualified by background, training and expertise in neurovascular treatment of IAs. The member(s) will not be an investigator on the study. The CEC will regularly review and adjudicate the adverse events and any deaths. Classification of the events will include device and procedure relatedness and seriousness. Member(s) will be provided data summaries and source documentation for review.

 Cerus Endovascular	Document Number DNQS428-01	Rev. F	Page 43 of 119
Clinical Investigation Plan	Title		
Confidential & Proprietary	Coil Assisted Flow Diversion: A prospective, single arm, multi-center study to assess the safety and performance of Neqstent in adjunctive therapy (CAFI Study)		

## 9.2 Data Safety and Monitoring Board (DSMB)

A DSMB will convene of member(s) experienced in an associated discipline. The DSMB will review the study data after enrollment of the first five patients. Enrollment of further patients will occur as the DSMB reviews the data. The DSMB will provide a report following the review and advise Cerus Endovascular for any modifications or concerns that may be necessary. The DSMB will provide further evaluation at least twice per year and after the first 5 patients are enrolled. If slow enrollment occurs, the DSMB may meet less frequently. The CEC and DSMB will meet as a combined committee.

## 9.3 Patient Selection Committee

A patient selection committee will provide guidance over the identification of all aneurysms in all eligible patients at each site to facilitate successful patient identification and implantation. The patient selection committee is a group of physicians who are trained and experienced users of Neqstent/Contour who have previous experience with embolization devices used in aneurysm treatment. The patient selection committee will have access to the patient images submitted by the investigator during the screening process. The patient selection committee will individually review and cast opinion on whether the proposed aneurysm is treatable with a Neqstent device per product specification guidelines. The web-based image system called CIMAR will be used to view and store images and patient selection committee's opinion on aneurysm suitability for treatment based on the Neqstent sizing guidelines or images will be viewed as forwarded by the treating physician. A minimum of two physician votes will be obtained and a third in the case of a tie.

## 10 Statistical Analysis

This study intends to examine the safety and performance of the Neqstent used for the treatment for embolization of intracranial aneurysms. The study is not powered to detect statistical significance. As such, clinical judgement is required to assess device safety and performance from the data collected during this study. Clinical judgement will be provided throughout the study by the DSMB.

### 10.1 Justification of Methodology

This study is designed as a single arm, descriptive study to develop further understanding of the Neqstent. It will provide safety and performance information for subjects from the Neqstent implantation to 24-month follow-up.

At one -month post procedure, the subjects will provide an adverse event profile related to the placement of the device. At six months of the study there will be additional information related to the adverse event profile including any device related instability or deficiency.

Similarly, the subjects will provide a performance profile. At six months post procedure, the information will provide how well the aneurysm has healed or embolized through the analysis of imaging performed by the independent core lab for accuracy and removal of bias. Note: In the

 Cerus Endovascular	Document Number DNQS428-01	Rev. F	Page 44 of 119
Clinical Investigation Plan	Title		
Confidential & Proprietary	Coil Assisted Flow Diversion: A prospective, single arm, multi-center study to assess the safety and performance of Neqstent in adjunctive therapy (CAFI Study)		

event of a Grade 2 or more using the Raymond Roy Scale, a second assessment will be made at 12- month follow-up to re-assess for complete occlusion and will be reported as a secondary efficacy.

## 10.2 Patient Population

Two patient populations will be considered in the analyses, an Intent-to-Treat (ITT) population and a Per Protocol population (PP). The ITT population includes all patients. The PP population will include subjects who complete 6 months of follow-up, die prior to their 6-month clinic visit, or are study failure (withdrawal from study to obtain alternate treatment). The PP will exclude patients with any major protocol violation that affects proper study inclusion or significant outcomes. Endpoints will be evaluated in the PP and ITT populations.

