## 10.4 Endpoints

### 10.4.1 Primary Endpoints

#### **Primary Safety Endpoint:**

The proportion of subjects with death of any non-accidental cause or any major disabling stroke within the first 30 days after treatment or major disabling stroke or death due to neurological cause from day 31 to 6 months after treatment.

Note: Major Disabling Stroke is defined as an episode of neurological signs or symptoms that persist beyond 24 hours accompanied with evidence of ischemia/infarction on imaging that results in an increase of NIHSS from baseline by  $\geq 4$  points and/or an increase from mRS baseline by  $>2$ .

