### Analysis Population

The safety population consists of all patients who are implanted with the study device. The primary analysis for all safety endpoints will be performed on this population.

The analysis for all primary and secondary study endpoints and baseline, procedural and follow-up characteristics will be performed on an intent-to-treat analysis population which will include all available data for all enrolled subjects. Standard summary statistics will be calculated for all study variables.

 Cerus Endovascular	Document Number DNQS428-01	Rev. F	Page 46 of 119
Clinical Investigation Plan	Title		
Confidential & Proprietary	Coil Assisted Flow Diversion: A prospective, single arm, multi-center study to assess the safety and performance of Neqstent in adjunctive therapy (CAFI Study)		

The primary safety endpoint will be calculated as the proportion of subjects with death of any nonaccidental cause or any major stroke within the first 30 days after treatment or major stroke or death due to neurological cause from day 31 to 6 months after treatment.

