#### **Endpoint Analysis:**

The primary performance endpoint will be calculated as the proportion of subjects with complete occlusion demonstrated with a Grade 1 on the Raymond Roy Scale at 6 months follow-up. In the event of a Grade 2 or more using the Raymond Roy Scale, a second assessment will be made at 12- month follow-up to re-assess for complete occlusion and will be reported as a secondary efficacy.

For AE reporting, both subject counts and event counts will be presented in tabular summaries of results.

A summary of subjects with protocol deviations will be reported but those subjects will be included in all analyses although endpoints may be summarized without the subjects (per-protocol analysis group) to provide additional information but not for the primary analysis.

For continuous variables, statistics will include means, standard deviations, medians and ranges. Categorical variables will be summarized in frequency distributions. Missing data will not be imputed. The number of data values available for each analysis will be reported so that the impact of missing data can be seen.

Statistical analyses will be conducted in SAS version 9.4 or above (SAS Institute, Cary, N.C.).

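### The Per Protocol rule in Section 10.2 has no route for a stroke survivor who withdraws before 6 months, so the supplementary PP safety rate can lose a known primary safety event

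*Combined protocol and SAP*

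**What the plan says.** **Membership of PP (Section 10.2).** "The PP population will include subjects who complete 6 months of follow-up, die prior to their 6-month clinic visit, or are study failure". Study failure is explained only by the bracketed gloss "withdrawal from study to obtain alternate treatment". Subjects with a major protocol violation are then taken out. The section closes: "Endpoints will be evaluated in the PP and ITT populations". It makes no exception for safety.

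**The safety endpoint (Section 10.4.1).** Besides deaths, the composite counts "any major disabling stroke within the first 30 days after treatment" and, later, "major disabling stroke or death due to neurological cause from day 31 to 6 months after treatment". A non-fatal stroke is therefore an event in its own right at any time up to 6 months.

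**Ways to leave early (Section 7.10).** Valid reasons include "AE or other medical condition that prevents study participation", withdrawal of consent and loss to follow-up. Each is listed separately from death.

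**Which population carries the primary safety result (Section 10.6, Analysis Population).** "The safety population consists of all patients who are implanted with the study device", and the primary analysis of every safety endpoint is assigned to that population. The same section analyses the endpoints on an ITT set that uses all available data from all enrolled subjects.

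**A second description of PP (Section 10.6, Endpoint Analysis).** Subjects with protocol deviations stay in all analyses, but "endpoints may be summarized without the subjects (per-protocol analysis group"). This is described as supplementary to the primary analysis. It has no 6-month completion rule and is not limited to major deviations.

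**The concern.** The endpoint has two kinds of event, death and major disabling stroke. Section 10.2 gives deaths before the 6-month visit an express route into PP and gives surviving stroke patients none. Take a subject with an adjudicated stroke on day 5 who leaves on day 40 because the deficit prevents participation, or who withdraws consent. That subject has not completed 6 months, has not died and has not left for alternate treatment. The outcome for the primary safety endpoint is settled, yet the subject is outside PP.

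The exclusion is unlikely to be unrelated to outcome. The endpoint requires an NIHSS rise of at least 4 points and/or an mRS rise of more than 2, and a deficit of that size is a plausible reason to stop attending. Since the rule already retains deaths and treatment failures, the omission looks like an oversight.

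At stake is how the PP safety rate is read. Section 10 leaves the assessment of safety to clinical judgement rather than a powered test, and the final report goes to the notified body (Section 12.1.15). A PP rate below the all-implanted rate could be taken as an effect of adherence when it reflects the removal of a known event.

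**Working it through.** **1. Reading the rule against the case.** A subject with a non-fatal major disabling stroke who exits before 6 months, other than for alternate treatment:

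| Text | Is the subject counted? |
|---|---|
| Section 10.2, completes 6 months | No |
| Section 10.2, dies before the 6-month visit | No |
| Section 10.2, study failure | No |
| Section 10.6, Endpoint Analysis, PP as subjects without deviations | Yes, if there was no deviation |
| Section 10.6, safety population | Yes |
| ITT | Yes |

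The two PP descriptions give opposite answers for the same subject.

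**2. Inputs.** Section 10.6 gives 51 enrolled, 10% attrition and 46 with 6-month data. Check: 51 × (1 − 0.10) = 45.9, or 46, hence 5 expected losses. The documents give no safety event rate and no PP count. The event counts below are assumptions, taken over a range of 1 to 5. All 51 are assumed implanted, with no exclusions for protocol violations.

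**3. Formulas.** Let N = 51 implanted, E = primary safety events, k = stroke survivors who leave early other than for alternate treatment, and d = event-free losses.

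- Safety population: E/N
- PP under Section 10.2 as written: (E − k)/(N − k − d)
- PP if subjects with a prior primary safety event are kept: E/(N − d)

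With d = 0, the drop caused by the rule is E/N − (E − k)/(N − k) = k(N − E)/[N(N − k)]. For k = 1:

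- E = 1: 50/(51 × 50) = 2.0 percentage points
- E = 5: 46/(51 × 50) = 1.8 percentage points

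**4. Results.**

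| E | k | d | Safety population | PP as written | PP with event subjects kept |
|---|---|---|---|---|---|
| 1 | 1 | 0 | 1/51 = 2.0% | 0/50 = 0.0% | 1/51 = 2.0% |
| 2 | 1 | 0 | 2/51 = 3.9% | 1/50 = 2.0% | 2/51 = 3.9% |
| 3 | 1 | 0 | 3/51 = 5.9% | 2/50 = 4.0% | 3/51 = 5.9% |
| 5 | 1 | 0 | 5/51 = 9.8% | 4/50 = 8.0% | 5/51 = 9.8% |
| 3 | 1 | 4 | 3/51 = 5.9% | 2/46 = 4.3% | 3/47 = 6.4% |
| 3 | 2 | 3 | 3/51 = 5.9% | 1/46 = 2.2% | 3/48 = 6.3% |
| 3 | 0 | 5 | 3/51 = 5.9% | 3/46 = 6.5% | 3/46 = 6.5% |

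The effect of the rule is the difference between the last two columns, about 2 points per affected subject. Comparing 3/51 with 1/46 would mix it with the loss of three event-free subjects from the denominator.

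**5. Precision.** In the first row the Clopper-Pearson 95% intervals are 0.0% to 7.1% for 0/50 and 0.0% to 10.4% for 1/51. The shift is small against sampling error, but it changes a table with one event into a table with none.

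**The case against.** The strongest reply is that nothing of consequence rests on this rate. Section 10.6 puts the primary safety analysis on all implanted subjects, where the stroke counts. ITT counts it too. The PP summary is optional in the Endpoint Analysis text and expressly not primary. The plan sets no PP safety threshold or test, and the combined CEC/DSMB adjudicates neurologic serious events whatever the analysis set. All of this stands. A reader might infer from Section 10.2 that the primary safety estimate is biased, and the documents do not support that.

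A reader might also infer that the PP safety rate is always too low. That does not follow either. The rule also removes event-free dropouts, which raises the rate: with 3 events and 5 event-free losses, PP is 3/46 = 6.5%, above 3/51 = 5.9%. The downward shift arises only if a subject with a non-fatal event actually leaves before 6 months for a reason other than alternate treatment. A survivor who stays remains in PP.

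Third, retaining dropouts who have events while excluding those who do not makes membership depend on outcome. That is a fair criticism of the main remedy, and it is why a second option is given below.

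None of this restores the subject to the Section 10.2 set. That section says endpoints will be evaluated in PP, whereas the Endpoint Analysis text only says they may be, so the two also differ on whether the analysis is planned.

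**Conclusion.** The point holds for the supplementary PP safety rate only, and only conditionally. As Section 10.2 is written, each survivor of a major disabling stroke who leaves before 6 months, other than for alternate treatment, takes one known primary safety event out of PP. At 51 implanted and 1 to 5 events this costs about 2 percentage points per subject. The event and withdrawal counts are assumptions, and the documents contain nothing from which to estimate how often this would happen.

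The conflict between Sections 10.2 and 10.6 does not depend on any assumed count. PP membership differs in the completion rule and in which deviations exclude a subject, so the reported PP rate could depend on which text the programmer follows. This is a wording correction to a secondary analysis, worth making before the data are analysed.

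**What to change.** 1. In Section 10.2, state that for the safety endpoint PP also includes any subject who had a primary safety event before withdrawal, whatever the reason for leaving. Alternatively, state that safety endpoints are reported only in the safety and ITT populations, which avoids outcome-dependent membership.
2. In Section 10.6 (Endpoint Analysis), replace the separate description of the per-protocol group with a reference to the Section 10.2 definition, including its restriction to major violations, and say whether the PP summary is planned or optional.
3. If PP safety is kept, show it beside the all-implanted rate with both denominators.

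The cost is wording only: no new data, visits or subjects. Under the first option the PP safety rate may look slightly less favourable. Because event-free dropouts stay excluded, it can also sit above the ITT rate (3/48 = 6.3% against 3/51 = 5.9% in the example with two such subjects), which is the reason for item 3.
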